### Secondary outcomes:

- Assessment of GI adverse effects determined by survey
- Analysis of CBC indices including reticulocyte count, MCV, etc.
- Iron studies at time of diagnosis
- Need for parental iron supplementation
- Need for transfusion in the peripartum period
- Postpartum hemoglobin and hematocrit
- Neonatal weight
- Presence of antepartum fetal growth restriction
- Neonatal outcomes such as NICU admission, hyperbilirubinemia, and APGAR scores
- Relationship of obesity to effectiveness of supplementation in both study arms

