## 14. Biostatistics:

We hypothesize that the intervention group will have a higher hemoglobin level in the third trimester than the standard group. The primary analysis will be conducted on an intention-to- treat basis. Between-group differences in continuous variables, will be assessed using Student t test or Man-Whitney rank sum test and results will be given as mean, standard deviation or median range as appropriate. Categorical variables will be assessed using the Pearson chi-square test or Fisher exact test as appropriate. For dichotomous endpoints, relative risk (RR) and 95% CI values will be calculated. P <0.05 will be considered significant. The analysis will be performed after study completion.

Based on our historical data at our center of 56 anemic women with iron deficient anemia that received standard daily iron supplementation: third trimester hemoglobin mean of  $10.27 \pm 1$  g/dL. We will first do a noninferiority approach. If noninferiority is not met, we will do a superiority analysis. For the noninferiority: If there is truly no difference between the standard and experimental treatment, then 68 subjects will be required to be 90% sure that the lower limit of a one-sided 95% confidence interval (or equivalently a 90% two-sided confidence interval) will be above the non-inferiority limit of -1. For the superiority: We estimate that a minimum sample of 39 per group, total N= 78 women will be needed to provide a power of 90% with a two-sided alpha level of 0.05 and a 1 g/dL difference in hemoglobin between control and intervention. We plan to enroll 86 patients in order to account for up to 10% missing data or loss to follow up. If no differences are noted among groups (non inferiority hypothesis failed) we will be performing a superiority approach. Stata 16 will be used for the statistical analysis.

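### One unadjusted P<0.05 rule covers about 12 named secondary comparisons on open-ended lists, so a false-positive secondary finding has roughly a one-third to one-half chance if the arms are equal

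*Combined protocol and SAP*

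**What the plan says.** Section 14 sets generic tests by type of variable. For continuous data: "Between-group differences in continuous variables, will be assessed using Student t test or Man-Whitney rank sum test". For categorical data: "Categorical variables will be assessed using the Pearson chi-square test or Fisher exact test as appropriate". It then gives one threshold: "P <0.05 will be considered significant". That sentence names no outcome. The only other significance level in the section, "with a two-sided alpha level of 0.05", belongs to the superiority sample-size calculation for hemoglobin.

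For dichotomous endpoints section 14 promises a relative risk with a 95% CI. For continuous outcomes it promises group summaries (mean and SD, or median and range) and a test, but no interval for the difference between arms.

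The secondary outcomes in section 1 are ten bullets. Two are open-ended: "Analysis of CBC indices including reticulocyte count, MCV, etc" and "Neonatal outcomes such as NICU admission, hyperbilirubinemia, and APGAR scores". One is not scored: "Assessment of GI adverse effects determined by survey". One is apparently a baseline measure: "Iron studies at time of diagnosis". The last concerns obesity and response in the two arms, and no analysis is given for it.

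The document contains no multiplicity adjustment, no ordering of secondaries, no key secondary outcome and no statement that secondary results are exploratory.

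**The concern.** A threshold that applies to every comparison lets any secondary result below 0.05 be called significant under the plan's own rule. With about a dozen comparisons, some such results are expected by chance: 12 × 0.05 = 0.6 on average when the arms do not differ.

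The open lists add to this. Section 3 describes the trial as open label, and section 4 has research staff and the PI following surveillance data by chart review while the trial runs. Section 12 defines the variables to be collected by pointing back to the outcomes, so it does not close the lists either. An index or neonatal outcome could be added by people who already know assignments and results, and it would still fit the plan.

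What is at stake is the credibility of secondary claims. The sample size rests on hemoglobin alone. Section 13 already names fewer GI side effects as an expected benefit of alternate-day dosing, and that outcome comes from a telephone survey of women who know their regimen. A chance finding on tolerance or a neonatal outcome could be reported as an established difference.

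**Working it through.** The plan states no family-wise error figure, so there is none to reproduce.

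**Count of tests.** Each item named in section 1 is counted once, and only if it is measured after treatment starts and compared between arms:

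- GI effects: 1
- Reticulocyte count, MCV: 2
- Parenteral iron: 1
- Transfusion: 1
- Postpartum hemoglobin, postpartum hematocrit: 2
- Neonatal weight: 1
- Fetal growth restriction: 1
- NICU admission, hyperbilirubinemia, APGAR: 3

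The total is 1 + 2 + 1 + 1 + 2 + 1 + 1 + 3 = 12. Iron studies at diagnosis are left out as baseline data, and the obesity item is left out because no test is defined for it.

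**Independent tests, all nulls true, 5% each.** Chance of at least one false positive = 1 − 0.95^12 = 1 − 0.540 = 46%.

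**Allowing for Fisher's test.** Five of the 12 are yes/no outcomes: parenteral iron, transfusion, growth restriction, NICU admission and hyperbilirubinemia. Section 14 permits Fisher's test, which is conservative for uncommon events. The event rates are not in the documents. At the planned 39 per arm, the exact size of the test is:

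| Assumed event rate | Actual size |
|---|---|
| 5% | 0.37% |
| 10% | 1.6% |
| 15% | 2.5% |
| 20% | 2.8% |

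With the other seven tests at 5% (0.95^7 = 0.698):

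- All five at a 5% event rate: 1 − 0.698 × (1 − 0.0037)^5 = 1 − 0.685 = 31%
- All five at a 20% event rate: 1 − 0.698 × (1 − 0.0276)^5 = 1 − 0.607 = 39%
- A mix (three at 10%, one at 5%, one at 20%): 36%

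**Allowing for correlation.** The documents give no correlations, so equal correlation ρ among 12 two-sided z tests was assumed and simulated (200,000 runs per value):

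| ρ | Chance of at least one false positive |
|---|---|
| 0 | 46% |
| 0.2 | 43% |
| 0.3 | 40% |
| 0.5 | 32% |
| 0.7 | 23% |

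The Fisher and correlation reductions were worked separately. Acting together they would lower the figure further. More tests raise it: for scale, 18 independent tests give 1 − 0.95^18 = 60%.

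**The case against.** The strongest reply is that the plan already separates primary from secondary outcomes in section 1, and that its hypotheses and sample size concern the primary alone. Most readers would take the secondaries as supportive. Dichotomous endpoints already get a relative risk with a 95% CI, and section 14 places the analysis after study completion. This stands in part. The primary analysis is untouched, and the missing interval affects continuous outcomes only. But the threshold sentence makes no such distinction, and analysing after completion does not close an open list.

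Three stronger readings are tempting, and the documents do not support them.

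- A reader might count 14 tests and conclude that a false positive is about as likely as not (1 − 0.95^14 = 51%). Reaching 14 needs either the obesity item taken as two within-arm associations, or that item counted once plus the baseline iron studies. Equal arms do not make a within-arm obesity association null: section 2 itself reports lower iron stores in obese patients. Iron studies at diagnosis precede treatment.
- A reader might add six tests by splitting GI effects into the seven complaints listed in section 2, giving 20 tests and 1 − 0.95^20 = 64%. That list is background. The survey's items and scoring are not in the document, so nothing shows that seven separate tests are planned.
- A reader might infer that secondaries will be reported with the same weight as the primary. The text leaves room for this but does not say it.

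**Conclusion.** The point holds at a moderate size. As written, the plan would let any of about 12 named secondary comparisons, or others added under the open lists, be called significant at an unadjusted 5%. If the arms are truly equal, the chance of at least one such false positive is roughly one third to one half.

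The upper end, 46%, assumes independent tests that each run at a full 5%. The lower figures rest on assumed event rates (5-20%) and correlations (0.2-0.5) that the documents do not supply. Stronger correlation would go below one third: 23% at 0.7, which is still more than four times the nominal 5%. Separate GI symptoms, several APGAR times or further CBC indices would push the figure up. The case for changing the wording does not depend on where in the range the true value lies.

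The point is about how secondary results may be claimed and says nothing against the validity of the primary analysis.

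**What to change.** Change the wording of section 14, with a matching clarification in section 1:

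- Reserve confirmatory claims for the prespecified primary analysis, meaning the noninferiority and superiority assessment of third-trimester hemoglobin. Limiting the claim to the superiority test alone would not work: section 14 runs superiority only when noninferiority is not met, so a trial that met noninferiority would have no confirmatory result.
- Say whether hematocrit is part of that primary analysis. Sections 1 and 4 name it alongside hemoglobin, but section 14 sizes and frames the test on hemoglobin only.
- Report every secondary outcome as a between-arm estimate with a 95% CI. For continuous outcomes this means adding a mean or median difference to the group summaries.
- Label secondary results as unadjusted and exploratory.
- Treat any outcome not named in section 1 as post hoc and report it as such.

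This needs no new data, visits or participants. The downside is that secondary results, including GI tolerance, can no longer be claimed as statistically significant.

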#### Outcomes

Our primary outcome will be change in hemoglobin and hematocrit in the 3rd trimester. Based on the available evidence with hypothesize that alternate day dosing of oral iron supplementation will be superior or at least not inferior to daily oral iron supplementation. Additionally we aim to assess the secondary outcomes as listed in the introduction obtained by chart review. Data to be collected includes population characteristics including demographics and data points described in the outcomes listed under the introduction obtained by chart review. A detailed explanation of the analysis of the primary outcome is described in a later section.

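### Superiority is tested only if non-inferiority fails, which is exactly when superiority cannot be shown, so the plan as written has no power for its own superiority hypothesis

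*Combined protocol and SAP*

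**What the plan says.** Section 14 sets the order of testing twice. The first statement puts the non-inferiority test first and continues: "If noninferiority is not met, we will do a superiority analysis". The second, after the sample-size figures, is "If no differences are noted among groups (non inferiority hypothesis failed) we will be performing a superiority approach". No other section gives a different order.

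Non-inferiority is judged by whether the lower limit of a one-sided 95% interval, which is the lower limit of a two-sided 90% interval, "will be above the non-inferiority limit of -1". The superiority calculation uses a two-sided 5% level, a 1 g/dL difference and 39 women per group for 90% power.

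Superiority is a stated aim. Section 14 opens with "We hypothesize that the intervention group will have a higher hemoglobin level in the third trimester than the standard group". Section 4 (Outcomes) expects that "alternate day dosing of oral iron supplementation will be superior or at least not inferior to daily oral iron supplementation", and section 1 poses the same two-part question.

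**The concern.** The usual sequence tests non-inferiority and, once it is met, goes on to superiority with the same interval. Section 14 does the reverse: a good result for alternate-day dosing ends the testing, and a poor one triggers a search for superiority.

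Two things are at stake. First, the formal conclusion that alternate-day dosing raises hemoglobin more is out of reach, although the larger sample size (78, raised to 86) was calculated to show it. Second, a trial that fails non-inferiority would go on to a superiority test. If that test is not significant, the result may be reported as no difference, which makes a negative finding look reassuring.

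The second statement of the rule adds a separate confusion. It treats finding no difference as the same thing as failing non-inferiority. Yet the same section powers non-inferiority to succeed when the true difference is zero.

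**Working it through.** **Inputs, all from section 14.** Margin -1 (printed without a unit, taken as g/dL of hemoglobin); non-inferiority at one-sided 5%; superiority at two-sided 5%; 39 per group; target difference 1 g/dL; SD 1 g/dL from the historical series. Let *d* be the observed difference (alternate-day minus daily) and SE = SD × √(2/39). With 76 degrees of freedom the t quantiles are 1.665 (90% interval) and 1.992 (95% interval).

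**The plan's own sample sizes.** Per-group n = 2 × SD² × (sum of z values)² / difference².

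- Superiority, SD 1: 2 × (1.960 + 1.282)² = 21.0, so 22 per group (44 in total). The plan says 39 per group.
- Non-inferiority, SD 1: 2 × (1.645 + 1.282)² = 17.1, so 18 per group (36 in total). The plan says 68 subjects.

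Neither figure follows from SD 1. Solving backwards, 39 per group implies an SD of √(39/2)/3.242 = 1.36. If 68 is a total (34 per group), it implies √(34/2)/2.926 = 1.41. That mismatch is a separate matter. Here SDs of 1.36 and 1.4 serve only as assumed values, to show that the conclusion does not depend on the SD.

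**The rule, algebraically.**

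- Non-inferiority fails if *d* - 1.665 SE ≤ -1, that is, *d* ≤ -1 + 1.665 SE.
- Superiority is shown if *d* - 1.992 SE > 0, that is, *d* > 1.992 SE.

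Because -1 + 1.665 SE is always less than 1.992 SE, no value of *d* satisfies both. This holds for any SD and, with the matching quantiles, any sample size.

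**In numbers, 39 per group.**

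| SD | SE | Non-inferiority fails if *d* is at or below | Superiority needs *d* above |
|---|---|---|---|
| 1 | 0.226 | -0.62 | +0.45 |
| 1.36 | 0.308 | -0.49 | +0.61 |
| 1.4 | 0.317 | -0.47 | +0.63 |

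**Simulation.** 200,000 trials per scenario, 39 per group, t-based intervals:

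| SD | True difference | Superiority concluded, as written | Superiority concluded, after non-inferiority is met |
|---|---|---|---|
| 1 | +1 | 0 | 99.2% |
| 1.36 | +1 | 0 | 89.4% |
| 1.4 | +1 | 0 | 87.7% |
| 1 | 0 | 0 | 2.5% |
| 1.36 | 0 | 0 | 2.5% |
| 1.4 | 0 | 0 | 2.5% |

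A normal approximation agrees. Power is Φ(1/SE - 1.96), which gives Φ(2.46) = 99.3% at SD 1 and Φ(1.19) = 88.4% at SD 1.4.

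**How often a failed non-inferiority test is followed by a non-significant superiority test.** This is the share of trials failing non-inferiority minus the share that also find daily dosing significantly better.

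| SD | True difference 0 | True difference -0.5 |
|---|---|---|
| 1 | 0.3% - 0.3% = about 0% | 29.33% - 29.31% = 0.02% |
| 1.36 | 5.7% - 2.3% = 3.4% | 51.6% - 35.8% = 15.8% |
| 1.4 | 6.9% - 2.5% = about 4.5% | 53.3% - 34.4% = 18.9% |

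This outcome becomes possible in practice when 1.992 SE exceeds 1 - 1.665 SE, that is, SE above 1/3.657 = 0.273, or an SD above about 1.2.

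**The case against.** The best defense is that section 14 also has a general sentence, with no gate, under which between-group differences in continuous variables are compared by t test or rank-sum test at the 5% level. Third-trimester hemoglobin is such a variable, so a superiority comparison might be produced anyway. This has some force: a p-value may well appear in the report. But the rule written specifically for non-inferiority and superiority makes the second depend on failure of the first. At best the section holds two conflicting instructions.

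Four narrower points are fair.

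- The planned superiority test is two-sided, so after failed non-inferiority it can still find daily dosing better (about 36% of trials at a true difference of -0.5 and SD 1.36). What it cannot find is the hypothesized benefit.
- Exact zero assumes the same mean-difference interval and population at both steps. With a rank-sum test at the second step the algebra no longer guarantees it, but a simulation at a true +1 g/dL and SD 1.36 found no case in 4,000 trials.
- The false-reassurance harm is negligible at SD 1 and matters only at SDs the plan does not state.
- The non-inferiority claim itself remains testable. What is lost is the formal superiority conclusion.

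None of these makes the written order workable.

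**Conclusion.** The concern holds. Under the rule stated twice in section 14, the probability of concluding that alternate-day dosing is superior is zero whatever the true benefit, SD or sample size, provided both steps use the same mean-difference interval and population. At 39 per group and a true +1 g/dL, reversing the order raises that probability to about 99% at SD 1, or 88% at SD 1.4, which is inferred from the 68 subjects and not stated. Equating no difference with failed non-inferiority is a further error. Because the rule governs the primary conclusion, it must be corrected. The trial is open label and is analyzed after completion, so a reversal made once results are known would look data-driven.

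**What to change.** Replace both statements of the testing order in section 14 with a single rule:

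> Non-inferiority is tested first. If it is met, superiority is tested on the same outcome and population, and is concluded if the lower limit of the two-sided 95% confidence interval for the difference (alternate-day minus daily) is above 0. If non-inferiority is not met, testing stops and the estimate and its confidence interval are reported.

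The sentence that equates no difference with failed non-inferiority is deleted.

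No alpha adjustment is needed, because every result that shows superiority also meets non-inferiority. That statement applies to one named endpoint. Sections 1 and 4 list change in hemoglobin and hematocrit, while section 14 works with third-trimester hemoglobin, so the rule should name the hemoglobin measure it applies to and give the margin its unit.

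The cost is two sentences, with no extra patients, data or alpha. The change should be made and dated before any comparison by group.

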## 3. Concise Summary of Project:

This trial will be a comparative pragmatic open label randomized controlled trial of daily versus alternate day dosing of oral iron in anemic pregnant patients.

Two randomly assigned groups will be compared during the antepartum period:

- 1. Control Group: standard of care, daily oral iron supplementation (325 mg PO daily ferrous sulfate)
- 2. Intervention Group: alternate day dosing oral iron supplementation (650 mg PO every other day ferrous sulfate)

325mg Ferrous sulfate is a standard oral iron supplement providing 65 mg of elemental iron per dose. Standard dosing recommendations for the treatment of iron deficiency anemia is between 65 to 200 mg elemental iron daily.

Each group will receive a phone survey 2-4 weeks after initiation of therapy to assess side effects of each group as well as compliance. Call is anticipated to last approximately 10-15 minutes. This survey has previously been validated in assessing gastrointestinal symptoms for those taking oral iron supplementation (33).

The number of subjects studied will be 86 subjects at UTMB, we plan to approach and consent up to 96 patients to allow for screening failures, early withdrawals, and patients lost to follow-up, and patients who must withdraw due to failure of therapy. Failure of therapy for the purposes of this study will be patients who require parental iron supplementation or transfusion. Study to last an anticipated length of 3 years. If our sample size is not achieved, we will submit to the IRB an addendum to increase the number of consented subjects to achieve the desired sample size.

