#### Additional details

The routine prenatal visits for pregnant patients with anemia include at least monthly venipunctures to monitor the treatment of anemia and intervene if necessary. Our primary outcome of 3rd trimester hemoglobin as well as laboratory secondary outcomes are convenient data points collected in the standard treatment and surveillance of anemia in pregnancy. As such patients will not need any study specific venipuncture or visits. Prenatal visits are frequent with monthly visits in the 1st trimester, bi-monthly visits in the 2nd trimester, and weekly visits in the 3rd trimester with 24 hour after hours care phone services available. The frequency and ready availability of appointments ensures that any symptomatic patient will quickly be seen and evaluated.

Any subject that requires escalation of treatment beyond oral supplementation (IV iron infusion or blood transfusion) will be referred to receive appropriate intervention. These subjects will still be included in the intent-to-treat analysis. The routine surveillance of anemic pregnant patients described above ensures that any treatment failure will be quickly identified and addressed.

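### Sections 3 and 14 use 86 as the number after losses and before losses respectively, and Section 3 treats as withdrawals the patients whom Section 4 keeps in the intention-to-treat analysis

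*Combined protocol and SAP*

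**What the plan says.** Section 14 (Biostatistics) sets the superiority requirement: "We estimate that a minimum sample of 39 per group, total N= 78 women". It then adds the loss allowance: "We plan to enroll 86 patients in order to account for up to 10% missing data or loss to follow up". The same section makes intention-to-treat the basis of the primary analysis.

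Section 3 (Concise Summary of Project) says: "The number of subjects studied will be 86 subjects at UTMB, we plan to approach and consent up to 96 patients". It gives four reasons for the larger figure: screening failure, dropping out early, loss to follow-up, and having to withdraw because therapy failed. It defines therapy failure as needing parenteral iron or a transfusion. It adds that, if the sample size is not reached, an addendum will go to the IRB to raise the number consented.

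Section 4 (Additional details) says of women who escalate to IV iron or transfusion: "These subjects will still be included in the intent-to-treat analysis".

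**The concern.** The same figure, 86, sits at two different points in the patient flow. In Section 14 losses are taken off it, and in Section 3 losses have already been taken off to reach it. Loss to follow-up is named in both steps. A reader cannot tell how many women are to be randomized, how many are expected in the analysis, or which count would trigger the IRB addendum.

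The second conflict concerns who is analysed. If women who fail oral therapy leave the study and the extra consents make up for them, the analysed group is selected on response to treatment. The trial is open label (Section 3) and escalation is left to the provider (Section 1, Brief Study Design and Rationale), so such departures could differ by arm. Need for parenteral iron and need for transfusion are also secondary outcomes (Section 1), so losing these women would lose the very events to be counted.

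**Working it through.** **Inputs.** Required number 78, loss up to 10%, enrolled 86 (Section 14). Number studied 86, consented up to 96 (Section 3).

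**Reproducing the plan's figures.**
- Section 14: 78 × 1.10 = 85.8, rounded up to 86. This matches.
- Section 3: 86 / 0.90 = 95.6, rounded up to 96. This matches a second 10% allowance on top of 86, although Section 3 does not say how 96 was reached.

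**The two patient flows side by side.**

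| | Before losses | After losses | Losses named |
|---|---|---|---|
| Section 14 | 86 enrolled | 78 needed | missing data, loss to follow-up |
| Section 3 | up to 96 consented | 86 studied | screening failure, early withdrawal, loss to follow-up, therapy failure |

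The number left after losses is 78 in one section and 86 in the other. Run end to end, the two steps allow for 96 − 78 = 18 losses, or 18/96 = 18.8%, against the single 10% stated in Section 14.

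**Can the step from 96 to 86 lie wholly before randomization?** Three of the four reasons in Section 3 normally arise after randomization. Section 4 (Screening, steps 3 and 4) puts randomization directly after consent. Section 9 screens charts for eligibility before consent and speaks of consent and randomization as one moment. Few women would therefore be lost between the two. On this reading, the number randomized is 86 under Section 14 and up to 96 under Section 3. The gap is at most 96 − 86 = 10 patients (10/86 = 11.6%). It is an upper bound, because the 96 also includes screening failures.

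**Does 86 cover a 10% loss?**
- In fractions, 86 × 0.90 = 77.4, and the exact inverse is 78 / 0.90 = 86.7, or 87.
- In whole patients, 10% of 86 is 8.6, so a loss of up to 10% is at most 8 (8/86 = 9.3%), and 86 − 8 = 78.
- Reaching 77 takes 9 losses (9/86 = 10.5%), which is outside the stated allowance.
- Even then, power for a 1 g/dL difference at two-sided 0.05 falls only from 90.0% to 89.6% at an SD of 1.345 (the value that 39 per group implies; the plan does not state it). It falls from 99.2% to 99.1% if the plan's ± 1 is read as the SD.

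**Therapy failures.** Section 3 names the same events, parenteral iron or transfusion, as reasons to withdraw. Section 4 names them as compatible with remaining in the analysis. A woman who stays in the analysis needs no extra consent to cover her.

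**The case against.** The best defence is that the plan describes one chain: up to 96 consented, 86 randomized, 78 analysed. The totals permit this, and 96 is a ceiling on patients approached and consented, not a randomization target. That is why the gap of 10 is only an upper bound. The defence does not remove the conflict, because Section 3 puts loss to follow-up and therapy failure in the step from 96 to 86, where this chain would have only losses before randomization.

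Two stronger readings are tempting, and the documents do not support them.

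- A reader might infer that 86 is too few, since a 10% loss leaves 77. In whole patients it leaves 78. Multiplying by 1.1 instead of dividing by 0.9 changes 86 to 87, which is a rounding matter. Under Section 3's reading no shortfall arises at all, since 96 × 0.90 = 86.4.
- A reader might infer that randomized women who fail therapy will be replaced, so that the intention-to-treat claim is already broken. No section says that anyone is replaced or removed from the analysis. Section 4 expressly keeps escalated women in, and Section 14 makes that analysis primary. Consenting extra women does no harm if everyone randomized is analysed. Replacement is an open question that the wording of Section 3 raises.

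**Conclusion.** The inconsistency stands as a minor point. The role of 86 differs between Sections 3 and 14, loss to follow-up is counted in both steps, and the number to randomize is uncertain by at most 10 patients. This assumes that enrolled in Section 14 means randomized, as the single consent-and-randomization visit suggests. Separately, Section 3's withdrawal of therapy failures conflicts with Section 4's retention of the same women. That matters more than the count, because it bears on who enters the primary analysis, but its effect on the result cannot be sized: the documents give no expected rate of escalation. There is no demonstrated loss of power and no demonstrated breach of intention-to-treat.

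**What to change.** State the consented, randomized and analysed numbers once and repeat them identically in Sections 3 and 14. One workable chain, for the sponsor to confirm, is up to 96 consented, 86 randomized and 78 analysed, with the allowance given as 8 of 86 (9.3%). Say which of these counts would trigger the IRB addendum.

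Reconcile Section 3 with Section 4 by stating that randomized women who escalate treatment stay in follow-up and in the intention-to-treat analysis and are not replaced. This concerns follow-up and analysis only; clinical management is left as it is.

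If 86 randomized is what the sponsor intends, the cost is wording, and Section 3's reasons for the 96 must be rewritten to match. If the sponsor meant 86 to remain after losses, that chain would cut the planned number randomized by up to 10, and the sponsor should instead write up to 96 randomized and 86 analysed. Keeping escalated women in follow-up needs no extra visits or blood draws, since the primary and secondary outcomes come from chart review of routine care (Section 8; Section 4, Additional details), apart from the phone survey already planned.
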